#### 9.3.4.3. Multiple Imputation

Missing data for the primary endpoint will be imputed utilizing multiple imputation methods. Multiple imputation provides a useful strategy for analyzing data sets with missing values. Instead of filling in a single value for each missing value, Rubin's [Rubin 1976, Rubin 1987] multiple imputation strategy replaces each missing value with a set of plausible values that represent the uncertainty about the correct value to impute.

The nature of missing data will be explored and the extent of missing data pattern (over time) will be summarized.

The assumption that data are missing at random (MAR) is common to the above analyses. To examine the primary endpoint with an analysis that does not require the MAR assumption, a pattern-mixture approach will be utilized for the imputation. The first step will be to apply a Markov chain Monte Carlo (MCMC) method [Schafer 1997] that assumes multivariate normality will be used to impute all missing values to make the imputed (resulting) data sets have strictly monotone missing patterns. The resulting monotone missing pattern will then, in a second imputation step, be used to impute the remaining missing values; specifically, a regression-based pattern-mixture method for continuous variables will be applied.

The SAS software system will be used to perform this imputation. Because the imputation of missing data is a key aspect to the analysis of the data, explicit details regarding this imputation are provided via sample SAS code that is intended to demonstrate the application of these strategies. Variable definitions are:

- TRT=treatment group (1 or 0)

- Eff1 is the first time point for the variable score
- Eff2 is the second time point for the variable score
- Eff\_last is the last time point for the variable score. Additional variable scores (between Eff1 and Eff\_last) would be included in this model according to the time points for collection.

The first step will be to impute partially in order to obtain a monotone missing data pattern.

```
proc mi data=DATAIN out=DATAIN_MONO nimpute=100 seed=123;  
  var TRT Eff1 Eff2 ... Eff_last;  
  mcmc chain=multiple impute=monotone;  
run;
```

The second step will be to impute the remaining (monotone) missing data that is MAR for each of the 100 imputed datasets from the first step.

Following the imputation of the data to create a monotone missing pattern, missing values for the earliest missing value (visitnum1) are imputed BY VISIT (thus, one imputation at a time), using the covariates basescore, MMSEbase score, geographic region, and previous score (ie, the non-missing score from previous visit). The first visit to be imputed (as necessary) would be the Week 4 time point, then the Week 24 time point. Thus, the process is repeated sequentially, by visit, until the monotone missing data pattern is completely filled in (imputed). In the case of the secondary endpoint, in which values are collected more frequently, there will be more ‘calls’ to the PROC MI procedure to generate the final imputed dataset. The following sample SAS code demonstrates the general methodology for imputing the first visit (Week 4) and second visit (Week 24) for UPDRS- III data. Note that the output dataset from the first imputation is used as the input dataset for the second imputation.

```
**First procedure imputes missing values for the first visit (Week 4);  
proc mi data=DATAIN_MONO out=DATAREG1 seed=465 nimpute=1;  
  by _Imputation_;  
  var visitnum1 bascore MMSEbase region previous;  
  monotone regression(visitnum1);  
run;  
  
** Second procedure imputes missing values for the second visit (Week 24)  
proc mi data=DATAREG1 out=DATAREG2 seed=465 nimpute=1;  
  by _Imputation_;  
  var visitnum1 visitnum2 bascore MMSEbase region previous;  
  monotone regression(visitnum2);  
run;
```

Note that the regressions do not include the treatment variable, and thus the imputed data at each time point will be based on the distribution of all data in the model rather than treatment-group specific distributions.

- A total of 100 imputed datasets will be created using these imputed data.
- Each of the 100 imputed datasets will then be analyzed using the MMRM model with effects for treatment, mmsebase score, region, and bascore. In this way, the test of the efficacy endpoint at Week 24 will be obtained, once for each of the 100 imputed datasets.
- The 100 resulting treatment effect parameters and standard errors from these will be combined to provide a distribution of parameters (and standard errors) upon which the sensitivity analysis will be concluded. PROC MIANALYZE may be used for this summary of the analysis.

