### 9.3.4. Sensitivity Analysis from Imputation of Missing Efficacy Data for Primary Efficacy Endpoint

#### 9.3.4.1. Cumulative Distribution Function

A cumulative distribution plot of changes in scores from baseline to Week 24 will be provided, with percent of patients on Y-axis and change score on X-axis.

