#### 9.3.4.2. Last Observation Carried Forward

An ANCOVA model will be run on the Week 24 data for which any missing values at Week 24 are imputed from last non-missing value carried forward (LOCF) for a given patient. If there are no on-treatment values for a patient, the baseline (last pre-treatment) observation will be carried forward.

*Sample* SAS code is as follows (where bascore is the baseline score for the endpoint and center is the pooled geographic region variable.

```
Proc Mixed data=dat;  
  Class treat MMSEbase center;  
  Model outcome=treat mmsebase center bascore;  
  Run;
```

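### SAP 9.3.4.3 presents the multiple imputation as free of the MAR assumption, but the procedure is a regression pooled over arms that the SAP itself calls MAR, and no controlled MNAR analysis is planned

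*SAP*

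**What the plan says.** The primary analysis (SAP 9.3.1) is an MMRM on observed UPDRS-III changes with treatment in the model and no imputation. SAP 9.3.4 lists three sensitivity analyses:

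- A distribution plot (9.3.4.1): "A cumulative distribution plot of changes in scores from baseline to Week 24 will be provided".
- An ANCOVA (9.3.4.2) in which "any missing values at Week 24 are imputed from last non-missing value carried forward (LOCF) for a given patient".
- Multiple imputation (9.3.4.3).

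Section 9.3.4.3 opens the argument with "The assumption that data are missing at random (MAR) is common to the above analyses" and then states the aim: "To examine the primary endpoint with an analysis that does not require the MAR assumption, a pattern-mixture approach will be utilized for the imputation". It says that, once the pattern is monotone, "a regression-based pattern-mixture method for continuous variables will be applied". Step 1 is MCMC with treatment in the variable list, and it only makes the pattern monotone. Step 2 is described as follows: "The second step will be to impute the remaining (monotone) missing data that is MAR for each of the 100 imputed datasets". Its regressions use baseline score, MMSE, region and previous score. The SAP says openly that treatment is not among them, so that "the imputed data at each time point will be based on the distribution of all data in the model rather than treatment-group specific distributions".

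SAP 9.4.1 applies the same three analyses to ADAS-Cog 11 and CIBIC+. The protocol (10.4.1) leaves missing-data detail to the SAP.

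**The concern.** Two sentences in one section describe the same imputation, one as not requiring MAR and the other as imputing data that are MAR. The text and sample code support neither the MAR-free claim nor the pattern-mixture label. A pattern-mixture analysis needs something that makes unobserved values differ from observed ones by dropout pattern, such as a shift, a reference arm or a pattern-specific model. None is given.

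Omitting treatment does move the MI away from the MMRM, which assumes MAR within arm. The size of that move is not chosen. It depends on dropout in each arm, on the effect of the other dose and on how much effect shows at Week 4.

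What is at stake is how the sensitivity result is read. If the MI estimate is weaker than the MMRM, pooling alone may explain it. If it holds up, the report could claim robustness without MAR when that was never tested.

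Few data could check the assumption directly. Subjects who stop study drug are withdrawn (Protocol 6.6.1), and efficacy values more than 7 days after the last dose are classed as follow-up, not Week 24 (SAP 7.7.2).

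**Working it through.** **Stated figure.** SAP section 6 gives 70 per arm, difference 4, SD 7.5, two-sided 0.05, power 88%. Check: 4 / (7.5 × √(2/70)) = 3.155; 3.155 − 1.960 = 1.195; Φ(1.195) = 0.884. It reproduces. It supplies only the effect and SD used below.

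**What fills a missing Week 24 value.** SAP 9.3.2 says UPDRS-III is collected at baseline, Week 4 and Week 24. Step 1 fills only gaps that precede a later observed visit. A missing Week 24 value is therefore always filled by the step 2 regression.

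**Inputs for the size.** From the SAP: effect E = 4, SD 7.5, three equal arms, 80 per arm. Assumed, because the documents give no values: both doses have effect 4; dropout d; correlation r of Week 4 and Week 24 changes from 0.3 to 0.7; Week 4 SD s from 5 to 7.5; Week 4 effect e from 0 to 2. Improvement is scored positive. Dropout is after Week 4 and MAR within arm. The 12.5% rate is what 70 out of 80 would imply if the gap is read as a dropout allowance.

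**Equal dropout.** Let p be the share of completers on active drug (2/3 here).

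- Pooled slope B = [r·s·7.5 + p(1−p)·e·E] / [s² + p(1−p)·e²]
- Planned MI estimate = (1−d)·E + d·B·e

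With e = 0 this is (1−d) × 4: 3.50 at 12.5% and 3.20 at 20%.

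With e = 2, s = 5, r = 0.7: B = (26.25 + 1.78) / (25 + 0.89) = 1.083, so B·e = 2.165. The estimate is 3.50 + 0.125 × 2.165 = 3.77 at 12.5%, and 3.20 + 0.20 × 2.165 = 3.63 at 20%.

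With the full effect at Week 4 (e = 4), the 12.5% range is 3.67 (r = 0.3, s = 7.5) to 4.02 (r = 0.7, s = 5). The shrinkage can vanish. An imputation that includes treatment returns 4.0 throughout.

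**Unequal dropout (assumed 10% placebo, 25% active; r = 0.5, e = 2).** Among completers p = 1.5/2.4 = 0.625, with mean Week 4 change 1.25 and mean Week 24 change 2.5.

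- s = 5: B = 20.625/25.9375 = 0.795. Imputed means are 2.5 − 0.795 × 1.25 = 1.506 (placebo) and 2.5 + 0.795 × 0.75 = 3.096 (active). Estimate = (0.75 × 4 + 0.25 × 3.096) − 0.10 × 1.506 = 3.62.
- s = 7.5: B = 30/57.19 = 0.525; estimate 3.54.
- Imputing by dose-placebo pair gives 3.46 to 3.56.

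The comparators are 4.0 (MAR within arm), 0.75 × 4 + 0.25 × 2 = 3.5 (LOCF) and 0.75 × 4 = 3.0 (placebo-reference).

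**Dependence on the other dose.** Suppose 35 mg is null, 70 mg has effect 4, there is no Week 4 effect, and dropout is 10% / 30% / 10% (placebo / 35 mg / 70 mg). The pooled mean is 0.9 × 4 / 2.5 = 1.44. The null dose is credited with (0.30 − 0.10) × 1.44 = 0.29 points.

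**Error rate and power.** Simulation with 80 per arm, 12.5% dropout, r = 0.5, 12,000 trials per setting, 30 imputations, Rubin's rules:

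| | Planned MI | MI with treatment | Placebo-reference |
|---|---|---|---|
| Rejection under the null | 2.8 to 3.1% | 5.0 to 5.1% | not run |
| Power (e = 2) | 85 to 86% | 89% | 82% |

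**What a tipping-point analysis would show.** Start from an estimate of 4.0 and worsen imputed values in both active arms by δ. The result loses significance where 4 − dδ = t·√[SE² + (2/80)(2/3)·d(1−d)·δ²], with d the active-arm dropout and t about 1.97.

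- 12.5% in each arm, SE 1.25: at δ = 10.9 the left side is 2.64 and the right is 1.97 × √(1.5625 + 0.217) = 2.63. The tipping point is about 11 points.
- 10% / 25%, SE 1.28: at δ = 5.6 both sides are 2.60.

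Holding the SE fixed would overstate these as 12.3 and 5.9.

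**The case against.** The strongest reply is that the SAP hides nothing. It says treatment is left out and what follows, so a planned result of about 3.5 to 3.6 in the unequal-dropout case does rest on a stated assumption, namely pooled conditional means. That stands. A reader might infer that the plan conceals the omission; it does not. What is wrong is calling the result free of MAR and pattern-mixture.

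Second, the practical difference can be modest. At 12.5% dropout with no Week 4 effect, the planned mean of 3.5 equals that of placebo-reference imputation. That also stands, but the match depends on equal dropout and no Week 4 effect. The larger contrast rests on assumed dropout of 10% and 25%, which no document supports.

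Third, LOCF is not a MAR method, so one planned analysis already departs from MAR. True, but it fixes each dropout at the last value, and its assumption cannot be varied. The Wilcoxon test, the distribution plot and the completer and per-protocol sets use observed values only. None is a controlled MNAR analysis.

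A reader might also infer that off-drug UPDRS-III data exist only for completers. Protocol 8.1 does limit Visit 13 to completers who do not enter the extension. The SAP schedule (Table 2), however, times that visit from Visit 12 or from early termination. These passages must be reconciled. On either reading the values are classed as follow-up and do not enter Week 24.

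**Conclusion.** The concern holds. The imputation in SAP 9.3.4.3 cannot serve its stated purpose, for the primary endpoint or for the two secondary endpoints that inherit it, and nothing else in the plan does so.

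Under the assumed inputs it lowers a true effect of 4 to 3.50 to 3.77 at 12.5% dropout and to 3.20 to 3.63 at 20%. It gives about 3.5 to 3.6 with 10% and 25% dropout, where explicit MAR and placebo-reference assumptions give 4.0 and 3.0. These sizes rest on assumed dropout, correlation and Week 4 values.

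A reader might infer that the primary conclusion or the type I error is at risk. The documents do not support that: the MMRM uses no imputation, the MI is supportive, and in the simulations it rejects a true null less often than 5%. The damage is to interpretation. This should be corrected before unblinding, but it does not undermine the primary test.

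**What to change.** Before unblinding:

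1. Delete the statements that this MI does not require MAR and is a pattern-mixture method. Describe it as regression imputation pooled over arms. Alternatively, replace it with a MAR imputation that includes treatment, noting that this will largely reproduce the MMRM and adds no robustness by itself. That replacement is optional and should not be made without item 2: in the 10% / 25% example it returns 4.0 even if active-arm dropouts lose all benefit and the truth is 3.0.
2. Prespecify one controlled MNAR analysis at Week 24: either a delta tipping point on imputed active-arm values, or placebo-reference imputation. Build it on an imputation model with treatment as a three-level factor (the sample code defines treatment only as 1 or 0). State whether it also applies to ADAS-Cog 11 and CIBIC+.
3. Correct the sentence that makes MAR common to the preceding analyses, and state that LOCF assumes a constant value after the last observation.

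The cost is SAP wording and a few lines of code, with no new data. The controlled result may look less favourable, and it is conservative if MAR holds: placebo-reference imputation gives 3.5 for a true 4 at 12.5% dropout. In the 10% / 25% case, simulated power is about 67%, against 86% for MI with treatment.

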#### **9.4. Analysis of the Secondary, Tertiary, and Exploratory Efficacy Endpoints**

Continuous variables will be analyzed in a fashion similar to that of the primary endpoint, using the MMRM methodology on the observed cases dataset as well as a Wilcoxon rank (nonparametric) test. For those endpoints that are collected only once on-treatment, as there are no repeated measurements, an ANCOVA will be used; however, it is intended that the PROC MIXED SAS procedure will be used in all cases to perform the analysis, as it is capable of both the ANCOVA and MMRM analyses.

When required, the ANCOVA will have effects for treatment, baseline variable score, baseline MMSE score, and geographic region. The observed case analysis will be considered the primary assessment of this variable.

No methods for imputation of missing values are planned for the exploratory endpoints. Exploratory endpoints will only be assessed using the MMRM analysis method.

#### 9.4.1. Secondary Efficacy Endpoint Analyses

The secondary efficacy analyses endpoints are the change from baseline in the ADAS-Cog 11 score at Week 24, and the observed scores of the CIBIC+ at Week 24.

This will be analyzed using similar MMRM methods as the primary endpoint (however, for the CIBIC+, no baseline value or interaction with visit will be included). A Wilcoxon Rank test will also be performed, as will the sensitivity analysis for LOCF to Week 24 and multiple imputation. The sensitivity analyses as being performed on the primary endpoint (CDF, LOCF, and multiple imputation) will be performed for the secondary endpoints.

For the CIBIC+, The number and percentage of subjects in each category of CIBIC+ will also be summarized by visit for each treatment group and tested using a CMH RMS test.

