### 3. STUDY DESIGN

This is a multi-center, double-blind, randomized, placebo-controlled, parallel-group study in patients with probable DLB who are either not receiving therapy for DLB or are receiving a stable regimen of standard therapy for DLB. The efficacy and safety of Intepirdine at doses of 70 mg and 35 mg daily will be evaluated over a 24-week treatment period. All subjects who are on stable doses of other therapies to treat cognitive deficits and/or hallucinations associated with DLB will continue to remain on them for the duration of the study.

Approximately 240 subjects will be randomized. The randomization ratio will be 1:1:1 (70 mg Intepirdine: 35 mg Intepirdine: placebo). Double-blind treatment will be administered as follows:

- 70 mg Intepirdine (Test therapy): Intepirdine 70 mg given as two tablets of intepirdine 35 mg
- 35 mg Intepirdine (Test therapy): Intepirdine 35 mg given as one tablet of intepirdine 35 mg and one tablet of placebo
- Placebo (Reference): Matching placebo, given as two tablets of placebo

The primary endpoint (UPDRS Part III) and the secondary endpoints (ADAS Cog 11 and CIBIC+) will be measured after 24 weeks of treatment. Study participation will last approximately 32 weeks: 0 to 4 weeks for Screening, a 2-week Single-Blind Run-In Period to evaluate baseline status, a 24-week randomized, double-blind, placebo-controlled Treatment Period and a 2-week Safety Follow-up Period for subjects who do not enter the extension study RVT-101-2002.

[figure not shown]
There will be weekly clinical assessments for the first two weeks of double-blind treatment, bi-weekly assessments thereafter until 12 weeks post-randomization and every six weeks thereafter. For certain visits (Visits 5, 7 and 9), subjects may have the option of whether to have assessments performed at the clinical study site or by a trained, visiting nurse in their own home.

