### **5.3. Clinician’s Interview Based Impression of Change Plus Care Giver Interview (CIBIC+)**

The CIBIC+ assessment [[Schneider 1997](#)] measures the global functioning of the subject through structured interviews by an investigator with both the subject and caregiver. The CIBIC+ is a secondary endpoint in this study. CIBIS is the baseline version.

The CIBIC+ is recorded on a 7-point scale with a score of 4 indicating no change, scores above 4 indicating worsening, and scores below 4 indicating improvement.

The CIBIC+ scale is a single item instrument, if the CIBIC+ is not done at a visit or the result is missing at a visit, the result will be set to missing. There is no ‘change from baseline’ calculated (eg, using the CIBIS). The CIBIC+ is analyzed by-visit using the observed values.

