## 6. SAMPLE SIZE CONSIDERATIONS

The sample size is based on assumptions of treatment benefit for one primary endpoint, the UPDRS- III total score. A sample size of 70 subjects per treatment group will allow a treatment difference of 4 points between placebo and active treatment in the change from baseline in UPDRS- III score to be detected with 88% power and a 0.05 significance level assuming an underlying standard deviation (SD) of 7.5

There are two secondary endpoints:

- ADAS-Cog 11 total score. A sample size of 80 subjects per treatment group will allow a treatment difference of 3 points between placebo and active treatment in the change from baseline in ADAS-Cog-11 score to be detected with 88% power and a 0.05 significance level assuming an underlying standard deviation (SD) of 6. Under the assumptions of a 2.5, 2.0 and 1.5 point treatment effect, the power is 74%, 55% and 35%, respectively.
- CIBIC+. A sample size of 80 subjects per treatment group will allow a treatment difference of 0.5 points between placebo and active treatment in the observed values in the CIBIC+ to be detected with 91% power and a 0.05 significance level assuming an underlying standard deviation (SD) of 0.95. Under the assumptions of a 0.4 and 0.3 point treatment effect, the power is 75% and 51%, respectively.

Randomization will be stratified according to Baseline MMSE score in the groupings of 14-17 points, 18-21 points and 22-26 points and according to whether subjects are or are not taking a cholinesterase inhibitor as a concomitant medication.

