## 7. GENERAL CONSIDERATIONS FOR DATA ANALYSES AND HANDLING

The primary statistical framework will be to test the superiority of Intepirdine over placebo. The null hypothesis is as follows, with a significance level of  $\leq 0.05$  needed for the null hypothesis to be rejected.

- There is **NO** statistically significant difference between Intepirdine and placebo in the mean change from baseline to Week 24 in the UPDRS- III.
- There **IS** a statistically significant difference between Intepirdine and placebo in in the mean change from baseline to Week 24 in the UPDRS- III.

The individual Intepirdine arms will be tested, as follows:

- Intepirdine 70 mg vs placebo
- Intepirdine 35 mg vs placebo

All hypothesis tests will be 2-sided, performed at the 5% level of significance.

The primary endpoint needs to achieve a significance level of 0.05 within an Intepirdine dose to allow for testing of the secondary endpoints within that dose.

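### Baseline CIBIS is collected but unused in the CIBIC+ model; prespecifying it as a covariate costs almost nothing and may add precision

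*SAP*

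**What the plan says.** SAP 9.3.1 gives the primary MMRM these terms: treatment, visit, treatment by visit, pooled region, baseline MMSE, the endpoint's own baseline value, and that baseline by visit. SAP 9.4.1 applies a similar model to both secondary endpoints, with one exception: "for the CIBIC+, no baseline value or interaction with visit will be included". Protocol 10.4.2 says the same. For CIBIC+ the two baseline-value terms drop out, while baseline MMSE and region remain.

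A baseline global rating does exist. The schedules in both documents place CIBIS at Visit 3, and SAP 5.3 states that "CIBIS is the baseline version". The same section says that no change score is formed from CIBIS and that CIBIC+ is analysed as observed at each visit. Protocol 8.3.1.4 explains why: CIBIC+ is already a rating of change from baseline, on a 7-point scale where 4 means no change.

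SAP 9.4.1 also sends CIBIC+ through the LOCF and multiple-imputation analyses. In SAP 9.3.4.2 and 9.3.4.3 both use a baseline score (`bascore`) as a covariate. The LOCF rule also carries the baseline observation forward when a patient has no on-treatment value. The SAP does not say what either baseline is for CIBIC+.

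**The concern.** That no change from CIBIS can be computed is a sound reason not to subtract it. It is not a reason to leave it out of the model. A severity rating taken before randomised treatment can be a covariate for a later change rating, and neither document explains why it is omitted.

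Baseline MMSE is not a complete substitute. MMSE measures cognition, whereas CIBIC+ rates global functioning in a disease that the protocol describes as having motor, behavioural and fluctuating features. CIBIS is the matching global rating. If it predicts Week 24 CIBIC+ beyond MMSE and region, the treatment comparison has a larger residual variance than it needs.

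There is also a practical gap. The main model uses no baseline for CIBIC+, while the two sensitivity analyses call for one that is undefined. A programmer would have to choose, and the LOCF text could be read as allowing a severity score to be entered as a change score.

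**Working it through.** **Inputs.** From SAP section 6: "CIBIC+. A sample size of 80 subjects per treatment group", a "treatment difference of 0.5 points between placebo and active treatment in the observed values in the CIBIC+ to be detected with 91% power", "assuming an underlying standard deviation (SD) of 0.95". For smaller effects: "Under the assumptions of a 0.4 and 0.3 point treatment effect, the power is 75% and 51%, respectively". From SAP section 7: "All hypothesis tests will be 2-sided, performed at the 5% level of significance". Allocation is equal, so each dose-placebo comparison is 80 against 80. The documents give no correlation between CIBIS and CIBIC+ and no dropout rate for this calculation. None was applied for dropout.

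**Step 1: reproduce the stated power.** The standard error of the difference is SD × √(2/n) = 0.95 × √(2/80) = 0.1502. Power by the normal approximation is Φ(δ/SE − 1.96), the other tail being negligible.

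- δ = 0.5: 0.5/0.1502 = 3.33, power 91.4% (noncentral t 91.1%; stated 91%)
- δ = 0.4: 0.4/0.1502 = 2.66, power 75.9% (t 75.4%; stated 75%)
- δ = 0.3: 0.3/0.1502 = 2.00, power 51.5% (t 51.0%; stated 51%)

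The plan's figures reproduce as a plain two-sample calculation with no covariate. They do not depend on CIBIS.

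**Step 2: effect of adding CIBIS.** Let r be the partial correlation of baseline CIBIS with Week 24 CIBIC+, given the terms already in the model. The residual SD becomes 0.95 × √(1 − r²), and the same precision without CIBIS would need 80/(1 − r²) patients per arm. The stated 0.95 is taken as the SD under the current model. The values of r are assumptions.

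| r (assumed) | Residual SD | SE reduction | Equivalent n per arm | Power at 0.5 | Power at 0.4 | Power at 0.3 |
|---|---|---|---|---|---|---|
| 0 | 0.950 | 0% | 80 | 91.4% | 75.9% | 51.5% |
| 0.1 | 0.945 | 0.5% | 81 | 91.7% | 76.3% | 51.9% |
| 0.2 | 0.931 | 2.0% | 83 | 92.5% | 77.6% | 53.1% |
| 0.3 | 0.906 | 4.6% | 88 | 93.7% | 79.7% | 55.3% |
| 0.4 | 0.871 | 8.4% | 95 | 95.3% | 82.8% | 58.7% |

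**Step 3: cost if CIBIS predicts nothing.** With about 240 patients, three arms and one added covariate, the variance of the treatment contrast inflates by roughly 1 + 1/(240 − 3 − 2) = 1.0043, about 0.4%. The gain offsets this when 1 − r² = 1/1.0043, that is r² ≈ 1/236, or r ≈ 0.065. The table does not deduct this small cost.

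**The case against.** The strongest reply is that the exclusion is deliberate, appears in both documents, and leaves a valid analysis. In a randomised comparison, omitting a covariate does not invalidate the test. Randomisation is stratified on baseline MMSE and cholinesterase inhibitor use, and MMSE and region stay in the model. All of this stands, and it limits the point to an optional gain in efficiency.

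Four stronger readings are tempting, and the documents do not support them.

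- *The endpoint certainly loses free precision.* No value of r is given. The raw correlation is also the wrong quantity: only association beyond MMSE and region counts, and it could be small. Up to r = 0.2 the gain at 0.5 points is about 1 percentage point or less.
- *A severity imbalance is left in the estimate as bias.* Any CIBIS imbalance after randomisation is chance, and adjustment for MMSE already removes the part shared with cognition.
- *CIBIC+ is the only scale not adjusted for its own baseline.* The CDR composite in SAP 5.13 is built from changes divided by the baseline SD, so its baseline is zero for everyone and carries no information.
- *CIBIS and CIBIC+ come from the same rater.* Protocol 8.3.1.4 asks sites to try for this; it does not guarantee it. CIBIS rates severity and CIBIC+ rates change, so CIBIS is not a like-for-like baseline as it is for ADAS-Cog 11.

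**Conclusion.** This is a low-severity improvement, not an error. The CIBIC+ MMRM is valid and its stated power reproduces without CIBIS. The plan may give up some precision by not using a rating it already collects. How much cannot be known from the documents: across assumed r from 0.1 to 0.4, power rises by 0.3 to 3.8 percentage points at the 0.5-point design effect and by 0.4 to 7.2 points at 0.3 points. The gain becomes material only from about r = 0.3. Set against this, the worst case is about 0.4% extra variance, so the balance favours prespecifying the covariate.

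These figures assume 80 evaluable patients per arm and a two-sample approximation to the Week 24 contrast. The undefined baseline score in the CIBIC+ sensitivity analyses does not depend on r and needs resolving in any case.

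**What to change.** Before unblinding, amend SAP 9.4.1 as follows.

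1. In the CIBIC+ MMRM, replace the dropped baseline terms with baseline CIBIS and CIBIS-by-visit. Keep MMSE and region.
2. State that `bascore` in the CIBIC+ LOCF ANCOVA, the imputation regressions and the post-imputation model is baseline CIBIS.
3. State that CIBIS is never carried forward as a CIBIC+ value under the LOCF rule, because it rates severity and not change. Say explicitly how LOCF handles a patient with no on-treatment CIBIC+.

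Protocol 10.4.2 carries the same exclusion. SAP 7.3 gives the SAP precedence where they differ, so the SAP edit is enough provided the difference is recorded. The Wilcoxon and CMH analyses of CIBIC+ are unaffected. The cost is a few sentences and minor programming, with no new data, visits or patients.
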